13.0 CRITERIA FOR REMOVAL FROM STUDY

- If at any time the patient develops recurrent or progressive disease (e.g. a new breast primary, loco-regional or distant recurrence) she will be taken off study and referred for conventional therapy.

- If at any time the patient develops unacceptable toxicity, defined as any Vagifem related toxicity greater than or equal to a grade three toxicity, she will be removed from study.
- If at any time the patient is found to be ineligible for the protocol as designated in the section on Criteria for Patient/Subject Eligibility (i.e. a change in diagnosis), the patient will be removed from the study.

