The primary analysis will focus on analyzing the change in estradiol level from baseline to 12 weeks using a two-sided paired t-test. We plan to recruit sixty eligible women, with the expectation that 48 (80%) will complete the study and be compliant. We plan to recruit 30 women who have been on anastrozole therapy and 30 women who have been on letrozole therapy. Patients who drop out due to self-withdrawal, recurrence or noncompliance will be eliminated from the primary analysis but will be examined closely. Patients are evaluable if they have at least baseline and week 12 values.

The primary analysis will be a two-sided paired t-test to evaluate whether there was a change in estradiol levels from baseline to 12 weeks. For a sample size of 48, we will be able to detect a difference of .41 or higher on a standard unit scale with 80% power and **5% type I error** using a paired t-test. To translate this into the scale commonly used to report estradiol, we examine a series of 6 breast cancer patients published by Kendall et al (2006). In Kendall et al, estradiol levels ranged from close to 0 to 5 pmol/l before starting vaginal estradiol, to close to 0 to 25 at 7 weeks. Based on these data, we conservatively estimate the standard deviation of the difference to be 7 (**roughly, range/4**). Thus, for a sample size of 48 we will be able to detect an absolute difference in estradiol of 2.88 pmol/l with 80% power and **5% type I error**.

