In addition to the main analysis described above, there are several secondary analyses planned for the FSH and FSFI/menopause checklist endpoints. Two-sided paired t-tests will be performed to evaluate change in FSH levels from baseline to 12 weeks and FSFI from baseline to 12 weeks and baseline to 24 weeks. To adjust for covariates of interest, such as type of aromatase inhibitor, an ANCOVA will be fit to the data. Trends of estradiol levels, FSH levels, and FSFI/menopause symptoms over the course of the study for all available timepoints will also be examined using graphical methods and repeated measures models. The graphs will illustrate patients and drug-specific short- and long term variations in estradiol (primary endpoint), FSH, and FSFI/menopause symptoms (secondary endpoints). It is hypothesized that estradiol levels will increase until approximately week 12 and then return to baseline after the vaginal walls reepithelialize. It is also hypothesized that FSH will remain constant throughout the 24 weeks and the FSFI/some menopausal symptoms will show improvement from baseline to both 12 and 24 weeks. To bring data from all these timepoints together, we will fit a repeated measures model²⁰ and if needed adjust our model to allow the time-effect to be modeled nonparametrically.²¹ Modeling the time-effect nonparametrically may be needed if estradiol trends over time, for example, do not have a simple parametric form such as a straight line or a quadratic curve. Model parameters and graphs of the raw data will help us identify where there are increases, decreases, or plateaus in estradiol, FSH, and FSFI over the study period. All these models can be fit in standard statistical software like SAS for Windows.

As in any prospective study, we expect missing data on a subject and item level. This is a small study, and thus, we do not plan to do any imputation. However, we will evaluate the degree of missingness in the final study by calculating attrition rates and the percent of missing values for a given variable. We will also examine the patient characteristics of the patients who have missing values. All analyses will be interpreted with missing data issues in mind.

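### The primary estradiol test drops women who leave before week 12, although the repeated-measures model already planned could use their week-2 and week-7 values; any resulting bias may run in either direction.

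*Combined protocol and SAP*

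**What the plan says.** Section 14.0 of the combined protocol and SAP sets the test: "The primary analysis will be a two-sided paired t-test to evaluate whether there was a change in estradiol levels from baseline to 12 weeks". A woman is evaluable if she has at least the baseline and week-12 values. Of 60 recruited, 48 (80%) are expected to complete and comply. For the rest: "Patients who drop out due to self-withdrawal, recurrence or noncompliance will be eliminated from the primary analysis but will be examined closely".

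These two rules do not quite match. A woman who has both values but leaves later, or is noncompliant, is evaluable under one and removed under the other.

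Estradiol is also drawn at weeks 2 and 7, so a woman who leaves before week 12 may already have one or two values on treatment. Section 14.0 plans a model that could use them: "To bring data from all these timepoints together, we will fit a repeated measures model". Its stated purpose is to describe trends. It is not tied to the week-12 change and is not named as a check on the primary test.

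On missing data: "This is a small study, and thus, we do not plan to do any imputation". Attrition rates, the percentage missing and the characteristics of women with missing values will be described. Sections 4.1 and 10.0 add that a woman who misses an assessment is contacted and, if still using the tablets, asked to return for an estradiol test.

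**The concern.** A paired t-test in completers estimates the change for all treated women only if leaving is unrelated to the week-12 change. The plan relies on that without saying so. Recruiting 60 to obtain 48 protects power, but it does nothing against bias if those who leave differ from those who stay.

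Section 1.0 states the hypothesis that estradiol is not elevated at 12 weeks. A distorted mean in either direction therefore bears on the study's main conclusion: too low gives false reassurance, too high a false alarm. The early samples that could correct part of the distortion are collected and modelled, but play no part in the primary estimate.

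The decision not to impute is no obstacle. A likelihood-based repeated-measures model uses each woman's observed values and imputes nothing.

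**Working it through.** **Inputs from section 14.0.** Two-sided 5% paired t-test, n = 48, 80% power; "we will be able to detect a difference of .41 or higher on a standard unit scale with 80% power"; "we conservatively estimate the standard deviation of the difference to be 7"; "we will be able to detect an absolute difference in estradiol of 2.88 pmol/l"; 60 recruited, 48 expected to complete and comply.

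**Step 1: the plan's own figures.** The noncentral t distribution with 47 degrees of freedom gives a detectable difference of 0.413 SD, and 0.413 × 7 = 2.89 pmol/l. Power at 2.88/7 = 0.411 SD is 79.7%. For recruitment, 48/0.80 = 60. The stated figures reproduce.

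**Step 2: how losing women shifts the mean.** If a share p is lost,

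bias of completers' mean = −p × (leavers' mean change − completers' mean change).

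- All 12 lost before week 12: p = 12/60 = 0.20. A gap of 3.5 pmol/l (half an SD) gives −0.20 × 3.5 = −0.70, so completers average 2.88 − 0.70 = 2.18.
- 6 lost: p = 0.10, and the same gap gives −0.35.
- 3 lost: p = 0.05, and it gives −0.175.
- A gap of −3.5 reverses each sign.

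**Step 3: simulation.** Assumptions not in the documents: changes at weeks 7 and 12 are bivariate normal with correlation 0.5 to 0.8; women leave after week 7; the log-odds of leaving move with the week-7 change by 0.5 to 1.0 per SD, in either direction. The SD is 7 and the true week-12 change 2.88 pmol/l. Completers' means are compared with the maximum-likelihood estimate that also uses week 7.

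| Women lost after week 7 | Bias of completers' mean, either sign (pmol/l) | Share of 2.88 | Reduction in SE from the model if leaving is unrelated to estradiol |
|---|---|---|---|
| 3 to 6 | about 0.1 to 0.5 | 3% to 17% | about 1% to 3% |
| 12 (upper bound) | about 0.4 to 1.1 | 14% to 38% | up to 7% |

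Shares: 0.1/2.88 = 3%, 0.5/2.88 = 17%, 0.4/2.88 = 14%, 1.1/2.88 = 38%. With all 12 lost and leavers tending to have higher week-7 changes, completers average 1.8 to 2.5. With the slope reversed, they can average up to 4.0. The model stays close to 2.88 either way.

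**Step 4: where the model falls short.** If leaving depends on the unseen week-12 value itself (12 lost, correlations 0.3, 0.5 and 0.7, weeks 2 and 7 both used), the completers' bias is about −1.36. The model's is −1.20, −0.95 and −0.63: smaller, but not removed.

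**The case against.** **Too many losses assumed.** The 12 expected losses cover every reason for not completing or complying over 24 weeks. Women who leave in weeks 13 to 24 can already have both values, and those who leave before week 2 have no value on treatment for the model to use. Only part of the 12 is likely to fall between weeks 2 and 12. This stands: the 12-loss row is an upper bound, not an expectation.

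**Direction.** A reader might infer that early leavers pull the result toward no elevation. In support, section 13.0 removes women for toxicity ("If at any time the patient develops unacceptable toxicity, defined as any Vagifem related toxicity greater than or equal to a grade three toxicity") and for recurrence, either of which might track absorption. The documents do not show that they do. Patients and investigators are blinded to the assay results for the 24 weeks (section 4.1), so nobody can leave because of a known rise. Section 3.0 reports that the 25 mcg dose gave both more relief and more absorption than 10 mcg. If the same link held within one dose (an assumption), low absorbers with little relief would leave and completers would overstate the rise. Dropping noncompliant, less exposed women would act the same way. This objection stands in full.

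**Already handled.** Calling women back reduces missing week-12 values, but reaches only those still using the tablets. Examining drop-outs and describing attrition does not correct the estimate. This stands only in part.

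**A paired t-test is conventional in a pilot.** True. A named sensitivity analysis would be an acceptable minimum.

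**Conclusion.** The point holds as a weakness of the primary estimate that wording can repair. Women who leave between weeks 2 and 12 are discarded although a planned model could use their data. If leaving is related to early estradiol change, the completers' mean is off by about 0.1 to 0.5 pmol/l with 3 to 6 such losses, and by at most about 0.4 to 1.1 pmol/l with 12. The sign is not fixed by the documents. If leaving is unrelated to estradiol, there is no bias and little precision is lost.

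These sizes rest on assumed correlations, slopes and timing of losses; only the SD, the target change and the counts come from the plan. Two stronger readings are not supported: that the analysis is biased toward finding no elevation, and that a bias of 14% to 38% of the detectable difference should be expected. The sample size calculation is not in question.

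**What to change.** In section 14.0, pre-specify the week-12 minus baseline estradiol contrast from the planned repeated-measures model as the primary estimate and test:

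- visit as a category, because the dosing frequency changes after week 2 and a straight line in time would not suit;
- unstructured covariance, with a stated fallback covariance and robust standard errors if it does not converge;
- every woman with a baseline and at least one estradiol value drawn while using the tablets.

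Keep the paired t-test as a sensitivity analysis. At minimum, make the model contrast a named sensitivity analysis reported beside the paired t-test. Reconcile the evaluability rule with the elimination rule, so that it is clear who enters the paired test.

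**Cost.** Wording only: no new visits, samples or patients. With complete data the unstructured model and the paired t-test agree, so the power statement carries over; a fallback covariance can change the standard error. The model relies on data being missing at random, a weaker assumption than the completers' test makes. It only reduces the bias if leaving depends on the unseen week-12 value, and it gains no on-treatment information from women who leave before week 2.

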4.0 OVERVIEW OF STUDY DESIGN/INTERVENTION

4.1 Design

This study is a prospective longitudinal pilot study measuring serum estradiol levels in 60 breast cancer patients in order to obtain 48 evaluable patients currently receiving treatments with adjuvant aromatase inhibitors. The goal is to have 30 patients on letrozole and 30 on anastrozole who are initiated on vaginal estrogen for symptoms of urogenital atrophy. Eligible women (see eligibility criteria section 6.0) seen in either breast medicine or gynecology clinic at MSKCC will be counseled on the use of low dose vaginal estrogens for symptomatic relief. A member of the clinical research staff will invite patients interested in using vaginal estrogens to participate in the study. After a patient elects to participate and provides informed consent, we will obtain serum to measure baseline estradiol and follicle stimulating hormone (FSH) levels. Patients will also complete the FSFI questionnaire. Patients will then receive a prescription for 10mcg vaginal 17- β estradiol.

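### The primary paired t-test leaves out the inhibitor type by which recruitment is planned; adding it to the model is a nearly free, minor gain in precision.

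*Combined protocol and SAP*

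**What the plan says.** Section 14.0 describes recruitment by drug: "We plan to recruit 30 women who have been on anastrozole therapy and 30 women who have been on letrozole therapy". Section 4.1 words the same split as a target: "The goal is to have 30 patients on letrozole and 30 on anastrozole who are initiated on vaginal estrogen for symptoms of urogenital atrophy". No cap or quota procedure is described. On numbers, section 14.0 states: "We plan to recruit sixty eligible women, with the expectation that 48 (80%) will complete the study and be compliant". Non-completers leave the primary analysis, and nothing is imputed.

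The primary analysis is then defined without reference to drug: "The primary analysis will be a two-sided paired t-test to evaluate whether there was a change in estradiol levels from baseline to 12 weeks". Its precision rests on one SD for all women: "we conservatively estimate the standard deviation of the difference to be 7".

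Inhibitor type enters later in section 14.0: "To adjust for covariates of interest, such as type of aromatase inhibitor, an ANCOVA will be fit to the data". That sentence is among analyses additional to the main one, in a paragraph that opens with the FSH and FSFI/menopause checklist endpoints. It does not clearly name estradiol and does not alter the primary test. The same paragraph plans drug-specific graphs, which do include estradiol.

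The protocol treats a drug difference as possible. Section 2.0 makes comparison of the estradiol rise between the two drugs a secondary aim. Section 3.0 reports stronger estradiol suppression with letrozole and leaves open whether levels take longer to settle on that drug.

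**The concern.** When group sizes are set by recruitment, a difference between the two groups' mean changes is not sampling error of the overall mean. A one-sample test on the pooled changes counts it as if it were, so its standard error is too large whenever the drugs differ. The design records the stratum and the primary test does not use it.

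An overly wide interval is usually a mild fault. It deserves a line here because the study hypothesis (section 1.0) is that serum estradiol is not raised at 12 weeks. Lost power leans, slightly, towards the hoped-for conclusion.

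**Working it through.** **Inputs.** From section 14.0: 48 evaluable women, two-sided 5%, 80% power, SD of the change 7 pmol/l. Assumed: equal evaluable groups (24+24) except where stated, and D, the between-drug difference in mean change, for which the documents give no value. I show D = 0, 2.88 (the plan's own detectable difference) and 5 pmol/l.

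**1. The plan's figure.** The plan states: "we will be able to detect a difference of .41 or higher on a standard unit scale with 80% power and 5% type I error". The noncentral t with 47 degrees of freedom gives a detectable effect of 0.4129 SD, and 0.4129 × 7 = 2.89 pmol/l, against 2.88 stated. Power at 2.88 is 79.7%. The figure is reproduced.

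**2. Variance.** With equal groups, total variance ≈ within-drug variance + D²/4.

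**3. If 7 is the within-drug SD.** The correct standard error is 7/√48 = 1.010. The pooled test uses, on average:
- D = 2.88: √(49 + 2.07) = 7.147; 7.147/7 = 1.021, so about 2% too large.
- D = 5: √(49 + 6.25) = 7.433; 7.433/7 = 1.062, so about 6% too large.

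Simulation (100,000 trials per setting, normal changes):

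| D (pmol/l) | Pooled: type I error | Pooled: power at 2.88 | Stratified: type I error | Stratified: power at 2.88 |
|---|---|---|---|---|
| 0 | 5.0% | 79.8% | 5.0% | 79.8% |
| 2.88 | 4.6% | 78.6% | 5.0% | 79.8% |
| 5 | 3.8% | 76.1% | 5.0% | 79.8% |

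**4. If 7 is the total SD.** The pooled test keeps its planned power whatever D is. Stratifying then uses the smaller within-drug SD, √(49 − D²/4), with 46 degrees of freedom and a multiplier of 0.4131:
- D = 2.88: √46.93 = 6.850; × 0.4131 = 2.83 pmol/l.
- D = 5: √42.75 = 6.538; × 0.4131 = 2.70 pmol/l.

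Both compare with 2.89 for the pooled test.

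**5. Cost if the drugs do not differ.** One degree of freedom: the detectable difference is 2.891 instead of 2.890 pmol/l.

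**6. Unequal evaluable numbers.** The pooled mean differs from a 50:50 average by (n₁/48 − 0.5) × D. At D = 2.88 this is 0.083 × 2.88 = 0.24 pmol/l for 28/20 and 0.125 × 2.88 = 0.36 for 30/18. An equal-weight average removes the shift, but its standard error is 3.5 × √(1/n₁ + 1/n₂): 1.025 at 28/20 and 1.043 at 30/18, against 1.010. When D = 0, power at 2.88 is then about 79% and 77%. Equal weighting has a smaller standard error than the pooled test reports only if D exceeds about 2.4 (28/20) or 3.7 (30/18).

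**The case against.** The strongest reply is that the plan contains no error. The 30/30 split is a goal, and the numbers analysed are whoever is evaluable. If the drug mix is not fixed, between-drug variation is legitimate sampling variation of the overall mean, and the paired t-test is a standard, correct test of it. That stands as a defence of validity. It does not remove the gain from using a recorded stratum to estimate the mean for the mix actually observed.

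The reply continues that the benefit cannot be sized from the documents. This also stands: D is unknown, the power loss in step 3 depends on reading 7 as a within-drug SD, and section 14.0 more naturally reads as the SD for the pooled test.

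Finally, the planned ANCOVA and drug-specific graphs would show a drug difference. They would, but they leave the primary standard error as it is.

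A reader might infer three stronger things that the documents do not support.
- *The primary test has a distorted error rate.* Type I error below 5% requires a zero overall mean with D not zero, so one group's estradiol must fall by D/2 while the other's rises by D/2. Nothing in the plan suggests this, and the error would be conservative in any case.
- *Unequal drop-out biases the primary mean.* Nowhere is a 50:50 average made the target. The primary aim concerns women on adjuvant aromatase inhibitors as a whole.
- *The primary estimate should be an equal-weight average.* Step 6 shows that this can lose precision in the very case it is meant to address.

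**Conclusion.** A minor improvement, not a defect. The paired t-test is valid and, with near-equal groups, slightly conservative when the drugs differ. The size rests on two quantities that the documents leave open. With a within-drug SD of 7 and 24+24 evaluable women, the loss is about one point of power at D = 2.88 and about four at D = 5. If 7 is the total SD, planned power is intact and stratifying offers a detectable difference smaller by 0.06 (2.89 − 2.83) or 0.19 (2.89 − 2.70) pmol/l. If D = 0, there is no effect. The case for changing is that the possible gain costs almost nothing.

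**What to change.** In section 14.0, define the primary analysis as a linear model of the baseline-to-week-12 change in estradiol on inhibitor type, with inhibitor type centred at its observed proportions among evaluable women. Test the intercept with the within-inhibitor residual variance. The point estimate is identical to that of the paired t-test. Report the mean change and confidence interval for each inhibitor alongside it.

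Keep the plain paired t-test as a supporting analysis. If evaluable numbers are unequal, also report the equal-weight average as supporting, and note its cost in precision.

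The cost is a sentence or two of text and one degree of freedom. No extra patients, visits or assays are needed, and the target of 48 evaluable women is unchanged.

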Low dose vaginal 17- β estradiol was shown to be highly effective in treating menopausal urogenital atrophy in women without cancer.² Vaginal 17- β estradiol was designed to relieve symptoms of urogenital hypoestrogenism with minimal systemic absorption and improved ease of usage compared to other vaginal estrogen formulations. In a study comparing 17- β estradiol to vaginal estrogen cream, both methods were equivalent for relief of atrophic vaginitis symptoms, but patients using vaginal 17- β estradiol had less systemic estrogen absorption, less endometrial proliferation and greater overall satisfaction.³ In another study, vaginal 17- β estradiol caused vaginal maturation, which gradually diminished absorption and systemic "spill over" of estradiol.⁴ In postmenopausal women after fourteen days of treatment, maturation of the vaginal epithelium occurred and absorption of estradiol subsequently declined significantly. FSH levels were unchanged during treatment with the 17- β estradiol. When systemic estradiol levels increase, FSH levels decrease correspondingly. Given the results of these studies, it was felt vaginal 17- β estradiol was efficacious and safe even for women trying to avoid estrogens. Recently a lower dose, 10 mcg 17- β estradiol, was FDA approved for postmenopausal women and is now readily available.

Despite the prevalence of urogenital symptoms in women with breast cancer, treatments have not been well studied in this population and are limited to over the counter lubricants, moisturizers, and dilator use with minimal impact. Vaginal 17- β estradiol was initially considered to be efficacious and safe even for women trying to avoid estrogens, and became widely prescribed to patients with breast cancer including women on endocrine therapy. Studies evaluating vaginal 17- β estradiol in postmenopausal women without breast cancer found only a transient increase in estradiol levels with return to baseline within twelve weeks. However, a recent prospective small observational study (n=6) performed by Kendall et al. demonstrated elevation in estradiol levels in 5 out of 6 women on aromatase inhibitors after two weeks of treatment with 25 mcg 17- β estradiol.⁵ After twelve weeks of therapy, estradiol levels decreased, but returned to pre-treatment levels in only 2 out of 6 women, which calls into question the safety of low dose 17- β estradiol in women with breast cancer. . The concern is that using low-dose vaginal estrogens

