may negate or diminish the effect of AIs. However, the small sample size renders it difficult to reach definitive conclusions, but it does underscore the need to perform a rigorous, adequately sized clinical trial to evaluate concurrent use of aromatase inhibitors and low dose 17- β estradiol. While it is clear that lowering estradiol levels as much as possible is ideal in preventing recurrences, the absolute estradiol level to minimize risk is unknown.

While the study suggests that this transient increase in estradiol may be of concern in this population, there is no clear evidence that a transient rise in estradiol causes any detrimental effects in patients with breast cancer. How much, if any, of these topical estrogens are absorbed through the mucous membranes of the vagina into the circulation is not known and the impact of low dose estradiol absorption on breast cancer outcomes is also unknown. Furthermore, the absorption will wane as the mucus membranes regenerate under estrogen exposure, which explains the return to baseline after 12 weeks noted in general population studies. In addition, since the vaginal mucosa of women using AI's has been even more depleted of estrogen exposure, it intuitively makes sense that a return to baseline will take longer. Therefore, this study will follow women for 24 weeks to see if longer therapy impacts estradiol level and systemic absorption. Finally, it is not known if the absorption of 17- β estradiol is different in the breast cancer population. It is therefore critical that we obtain further information regarding the safety of 17- β estradiol, an apparently efficacious treatment, in patients with breast cancer being treated with AIs. Since the risk/benefit of 17- β estradiol has not been rigorously evaluated and the lower 10mcg is now available, it was felt that evaluating the lowest possible dose for efficacy is the logical first step. We hypothesize that the systemic absorption of estrogen might be less with the 10mcg 17- β estradiol than with the 25mcg 17- β estradiol.

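### The planning SD of 7 pmol/l is called conservative, but range/4 from six patients understates the SD of those same data, so the 2.88 pmol/l sensitivity figure lacks support

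*Combined protocol and SAP*

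**What the plan says.** Section 14.0 (Biostatistics) specifies a two-sided paired t-test of the change in estradiol from baseline to week 12, with 48 evaluable women out of 60 recruited. It gives sensitivity first in standard units: "we will be able to detect a difference of .41 or higher on a standard unit scale with 80% power". It then converts this to pmol/l using a published series of six breast cancer patients, in which "estradiol levels ranged from close to 0 to 5 pmol/l before starting vaginal estradiol, to close to 0 to 25 at 7 weeks". From those figures it says "we conservatively estimate the standard deviation of the difference to be 7", with roughly range/4 in brackets as the only derivation, and concludes that "for a sample size of 48 we will be able to detect an absolute difference in estradiol of 2.88 pmol/l with 80% power". It gives no SD of paired differences, no interval for the SD and no alternative values.

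Section 3.0 (Background and Rationale) describes the same series. Estradiol was raised in "5 out of 6 women on aromatase inhibitors after two weeks of treatment with 25 mcg", and later: "After twelve weeks of therapy, estradiol levels decreased, but returned to pre-treatment levels in only 2 out of 6 women". The trial itself uses 10 mcg.

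**The concern.** In a sample size section, a conservative SD is one chosen large enough that the stated power is unlikely to be overstated. Dividing a range by 4 suits samples of about 25 to 30 normal values. In a sample of six the extremes lie closer together, and the same divisor gives a value that is too small. The label therefore runs against the rule used to get the number.

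The figure of 2.88 pmol/l is the plan's only statement of sensitivity in estradiol units, and the protocol summary hypothesizes no elevation at week 12. A reader of a non-significant result may judge it against 2.88. If that figure is believed to be cautious when it is not known to be, a null result will look more reassuring than the plan can justify.

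**Working it through.** **Inputs.** From section 14.0: n = 48, two-sided 5%, 80% power, 0.41 SD, SD 7 pmol/l, range/4, six patients, and levels of about 0 to 5 (baseline) and 0 to 25 (week 7). From section 3.0: 25 mcg in the series.

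**1. The plan's own figure.** Noncentral t with 47 degrees of freedom gives 80% power at 0.4129 SD. Then 0.4129 × 7 = 2.89, and the rounded 0.41 × 7 = 2.87. Power at 2.88 with SD 7 is 79.7%. The stated 2.88 reproduces to rounding.

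**2. Smallest SD for six values with range R.** The sum of squares is smallest with one value at each extreme and four at the midpoint: 2 × (R/2)² = R²/2. Dividing by n − 1 = 5 gives R²/10, so the sample SD is at least R/√10 = R/3.16. This needs no distributional assumption. For general n the minimum is R/√(2(n − 1)), which equals R/4 at n = 9. With six values, R/4 is always below the sample SD.

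**3. The same under normality.** Six normal values have a mean range of 2.534 SD, so range/4 averages 2.534/4 = 0.63 of the true SD. It falls below the true SD in about 95% of samples. The individual values are not in the documents, so normality cannot be checked.

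**4. What the quoted levels allow.** Take close to 0 as 0.
- The woman at 25 in week 7 rose by 20 to 25. The woman at 0 in week 7 changed by between −5 and 0.
- The range of the six differences is therefore at least 20 − 0 = 20 and at most 25 − (−5) = 30.
- The smallest possible sample SD is 20/3.162 = 6.3. The largest, with three values at each extreme of a range of 30, is 30 × √0.3 = 16.4.
- A sample SD of 7 needs a range of no more than 7 × 3.162 = 22.1. The quoted levels permit that, but range/4 would then be at most 22.1/4 = 5.5, not 7.

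**5. Size, as illustration only.** This assumes that the trial's SD equals the series' sample SD.

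| Range of differences | Sample SD at least | Detectable difference at least | Power at 2.88 at most |
|---|---|---|---|
| 25 (rounding 25/4 = 6.25 up to 7) | 25/3.162 = 7.91 | 0.4129 × 7.91 = 3.3 | 70% |
| 28 (back-calculated as 7 × 4; not in the documents) | 28/3.162 = 8.85 | 0.4129 × 8.85 = 3.7 | 60% |

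**6. Match to the endpoint.** Section 14.0 quotes ranges of levels, while the test uses within-patient differences. The levels are from week 7 and the endpoint is week 12. The series used 25 mcg and the trial uses 10 mcg. Section 3.0 reports lower levels by week 12 and hypothesizes that "systemic absorption of estrogen might be less with the 10mcg" tablet, which could mean a smaller SD. Section 14.0 also expects estradiol to rise until about week 12, which points the other way.

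**The case against.** The best defence is that the label describes the SD for this trial rather than the divisor. The data come from a higher dose and an earlier week, when levels were higher, so 7 may well exceed the spread at week 12 on 10 mcg. That is plausible, but section 14.0 does not argue it, and its own expectation of a rise until about week 12 weakens it. Rounding 6.25 up to 7 does not rescue the label either, because a range of 25 already forces a sample SD of at least 7.91.

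A reader might infer that 7 is too low and that the trial is underpowered, with power at 2.88 no better than 60% or 70%. The documents do not support this. Those figures are limits only if the trial's SD equals the sample SD of six women on another dose at another week. The range of 28 is stated nowhere. The quoted levels still allow a sample SD of 7. Even with a true SD of 7, six normal differences would span 25 or more in about 12% of samples, and 20 or more in about 33%. If the trial's SD were 6, power at 2.88 would be 90%.

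It also stands that the consequence is small. This is a pilot, section 14.0 openly discloses the six patients, week 7 and range/4, and 0.41 SD does not depend on the value 7. No margin or decision rule uses 2.88, and section 3.0 says that "the absolute estradiol level to minimize risk is unknown".

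**Conclusion.** The claim of conservatism is unsupported, and so is 2.88 pmol/l as a cautious detectable difference. That range/4 understates the SD of the six values it is taken from is algebra and holds for any distribution. Whether 7 is too low or too high for this trial is unknown, since the mismatches in quantity, week and dose could move the SD either way. Over SDs of 5 to 12 pmol/l, the detectable difference at n = 48 runs from 2.1 to 5.0 pmol/l. The 0.41 SD statement, the paired t-test and the sample size are unaffected. Severity is minor.

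**What to change.** In section 14.0:
1. Delete the word *conservatively*.
2. State that the SD of 7 is a rough range/4 value from six women, based on ranges of levels at week 7 on 25 mcg, and that the SD of week-12 differences at 10 mcg is unknown in both directions.
3. Keep 0.41 SD as the primary sensitivity statement.
4. Replace the single 2.88 with a short table for n = 48, two-sided 5%:

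| SD (pmol/l) | Detectable difference at 80% power (pmol/l) | Power at 2.88 |
|---|---|---|
| 5 | 2.1 | 97% |
| 6 | 2.5 | 90% |
| 7 | 2.9 | 80% |
| 8 | 3.3 | 69% |
| 10 | 4.1 | 50% |
| 12 | 5.0 | 37% |

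Items 1 to 3 are enough to correct the error; the table makes the uncertainty visible. The cost is a few sentences and one table, with no change to sample size, visits or analysis. The downside is a less precise and possibly less favourable stated sensitivity.
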